Title of clinical trial	Ultra-portable rapid-dispersal buccal lyophilised naloxone for constant carriage: testing in healthy volunteers
Protocol Short Title/Acronym	Buccal naloxone testing in healthy volunteers (NalBuc)
Trial Phase	Phase 1 Pharmacokinetic Study
(Co-)-Sponsor(s) name	King's College London and South London and Maudsley NHS Foundation Trust
Chief Investigator	[name] [name]
IRAS number	1011060
REC number	25/LO/0701
Medical condition or disease under investigation	Opioid overdose
Purpose of clinical trial	To study the absorption of different formulations of naloxone in healthy volunteers who will receive both this novel buccal naloxone wafer versus current forms of naloxone, with attention to the speed of absorption and best dose for future medicinal products.
Primary objective	To characterize and compare the pharmacokinetic profile of a novel buccal formulation of naloxone in healthy volunteers with approved formulations (naloxone ampoule) as the injectable form, and Nyxoid® as naloxone nasal spray comparison.
Secondary objective (s)	 To measure the dose-proportionality of the novel formulation by comparing the plasma exposure of two different buccal doses and one sublingually. To assess the safety and tolerability of the novel buccal formulation
Trial design	Phase 1 CTIMP. Pharmacokinetic study. Open-label, within-subject, repeated-sessions, random sequence, two-stage design. Stage 1 uses a five-way crossover design for treatment selection.

	Stage 2 uses another crossover design when at least one of the three novel formulations of naloxone meets the treatment selection criteria, otherwise, the study will be terminated.
Primary Endpoint	Time to Maximum Plasma Concentration - T _{max} measured from baseline to 4 hours post.
Secondary Endpoints	Time to 50% of maximum concentration -T50%, measured from baseline to 4 hours post.
	Maximum Plasma Concentration - C _{max} , measured from baseline to 4 hours post.
	Elimination Half-life - $T_{1/2}$ measured from baseline to 4 hours post.
	Area Under the Curve from time zero to 15 minutes, measured from baseline to 15 minutes post-dose.
	Area Under the Curve from time zero to infinity - AUC _{inf} measured from baseline to 4 hours post.
Sample size	12 participants in Stage 1.
	30-35 participants in Stage 2. Participants that partake in stage 1 will not be eligible to also participate in stage 2.
Summary of eligibility criteria	 Inclusion criteria I.01. Healthy volunteers. Defined as healthy based on a clinical history, physical examination, ECG, vital signs, and laboratory tests of blood and urine. I.02. Age 18-60 I.03. Able and willing to provide written informed consent I.04. Adequate venous access and willingness for intravenous cannulation during each visit.
	 Exclusion criteria E.01. Clinically relevant medical history, physical findings, ECG, or laboratory values at the pretrial screening assessment that could interfere with the objectives of the trial or the safety of the participant. E.02. Presence of acute or chronic illness or history of chronic illness sufficient to invalidate the
	volunteer's participation in the trial or make it unnecessarily hazardous. E.03. Impaired endocrine, thyroid, hepatic, respiratory or renal function, diabetes mellitus, coronary heart disease, or history of any neurological or mental illness.

- E.04. Surgery or medical condition that might affect the absorption of medicines.
- E.05. Blood pressure and heart rate in the supine position at the screening examination outside the ranges: blood pressure 90–140 mm Hg systolic, 40–90 mm Hg diastolic; heart rate 40–100 beats/min. Repeat measurements are permitted if values are borderline (i.e. values that are within 5 mm Hg for blood pressure or 5 beats/min for heart rate) or if requested by the investigator. Subjects can be included if the repeat value is within range or still borderline but deemed not clinically significant by the investigator.
- E.06. Loss of more than 400 mL of blood during the 3 months before the trial, e.g. as a blood donor.
- E.07. Any prescribed medication (apart from contraceptives).
- E.08. Use of any over-the-counter medications containing codeine or other opioids, prescribed opioid medication, or illicitly obtained opioids within the past 2 weeks (if the participant is taking a long-acting opioid the period might, after consideration by the examining doctor, be extended to 4 weeks or longer according to the washout period).
- E.09. BMI <18 or >30.0kg/m2.
- E.10. Intake of more than 14 units of alcohol weekly.
- E.11. Pregnant or breastfeeding.
- E.12. Women of childbearing potential (as defined in CTFG guidelines, see 6.7 Concomitant Medication) not willing to use a highly effective form of contraception (as defined in CTFG guidelines, see section 6.7 Concomitant Medication) during participation in the study or male patients not willing to ensure the use of a condom during participation in the study.
- E.13. eGFR≤ 70 ml/min.
- E.14. Any liver function or renal function test abnormality. A repeat is allowed on one occasion for determination of eligibility.
- E.15. Urine drug screen positive for any substances.
- E.16. Positive alcohol breath test, above 0.

	 E.17. Participant in any other clinical trial or experimental drug study in the past 3 months E.18. Known hypersensitivity to naloxone and/or formulation excipients (gelatin, mannitol). E.19. Not willing to ingest fish-derived gelatin. E.20. Insufficient understanding of the trial.
IMP, dosage and route of administration	A novel rapid-dispersal ultra-portable formulation of naloxone-at two test doses (2mg and 4mg) administered for buccal absorption in the cheek pouch, and a 2 mg dose administered sublingually. After the initial 12 participants in stage 1, IMP will be compared to active comparators to ensure relevance and competitiveness. IMP treatment arms may be discontinued for stage 2 following this review.
Active comparator product(s)	Naloxone ampoule of 0.4mg/1mL Intranasal naloxone 1.8mg/0.1mL (Nyxoid®)
Maximum duration of treatment of a participant	Single dose/arm Maximum three months duration/participant (expected)

2. Protocol Version History

Version Number	Date	Reasons for Update

3. Glossary of Terms

AE Adverse Event AR Adverse Reaction

AUC₀₋₁₅ Area Under the Curve from time zero to 15 minutes AUC_{inf} Area Under the Curve from time zero to infinity

BP Blood Pressure
CA Competent Authority
CI Chief Investigator

Cmax Maximum Plasma Concentration CRA Clinical Research Associate

CRF Case Report Form
CRF Clinical Research Facility
CTA Clinical Trial Authorisation

CTIMP Clinical Trial of Investigational Medicinal Product

DSUR Development Safety Update Report

EC European Commission
EU European Union
FBC Full Blood Count

FDA Food and Drug Administration
FSH Follicle-stimulating Hormone
GCP Good Clinical Practice

HR Heart Rate

IB Investigator Brochure ICF Informed Consent Form

IM Intramuscular

IMP Investigational Medicinal Product

IMPD Investigational Medicinal Product Dossier

IN Intranasal

IUD Intrauterine Device

4.1. Background & Rationale

Opioids continue to be the substances with the highest contribution to severe drug-related harm, including fatal overdoses (1). Opioid overdoses account for an estimated 150,000 global deaths annually and approximately 3,000 across the UK, representing a significant public health crisis (2). Opioids act on the central nervous system to stimulate opioid receptors in the brain and body, which intercept pain signals. (3) However, they can also cause respiratory depression, which in cases of overdose can lead to hypoxia, brain damage, and death (4). Opioid overdose is both preventable and if witnessed, treatable (reversible) (1).

Naloxone is a potent opioid antagonist that rapidly reverses the effects of opioid overdose (4). It actively displaces opioids from the mu-opioid receptor (MOR), effectively displacing and reversing their effects, particularly respiratory depression (5). Naloxone in injectable form has been used in clinical settings since the 1970s and has a well-established safety profile (6). Its effectiveness in reversing opioid overdose is well-documented, with the potential to restore normal breathing within 2-3 minutes of administration (7,8).

The US Food and Drug Administration (FDA) approved naloxone in 1971 as a prescription-only medication for intravenous (IV), intramuscular (IM), and subcutaneous (SC) administration to reverse the effects of opioids (9,10). It was subsequently adopted in international clinical practice and included in the World Health Organization's Model List of Essential Medicines in 1983 as a specific antidote (0.4 mg in 1mL ampoules) and has been continuously available across the UK and many other countries in injectable forms since the early 1980s (1,11). Due to its unique effectiveness and safety profile, naloxone has become the preferred treatment for reversing opioid overdoses in hospital emergency departments and ambulance services (10).

However, the life-saving potential of naloxone is critically dependent on its availability and prompt administration during an overdose event (12). Recognizing this, many countries have implemented take-home naloxone programs, providing the medication to individuals at risk of overdose, their friends and family members, and community workers. These programs have shown promising results in reducing opioid overdose mortality (13,14).

Nonetheless, the use of injections in emergency situations is limited by public and political apprehension about the wider use of injectable medication as well as the training required for proper administration and the lack of portability of syringes (15). Therefore, alternative non-injectable options need to be considered (8,16). More recently, since 2017, nasal sprays have been introduced, offering a needle-free option that is easier for lay persons to administer (6,17). The main forms currently in the UK are 'Prenoxad' (pre-filled syringe, 5 x 0.4mg doses) and 'Nyxoid®' (naloxone 1.8mg/0.1mL nasal spray, twin-pack) and, recently, generic nasal spray (1.26mg, also twin-pack) (18,19). However, these products are not convenient for constant carriage and have limited flexibility of dose which may prove insufficient for future overdose crisis situations (20). Similarly, their effectiveness can be compromised in cases where nasal passages are blocked or damaged (8).

Despite these options, significant barriers persist with the sought-after benefit from naloxone pre-provision (8,21,22). A key issue is the low carriage rate, with studies indicating that only 15-20% of those provided with naloxone consistently carry it (23,24). This low rate significantly reduces the likelihood of naloxone being available when an overdose occurs (20).

This study will evaluate a novel buccal formulation of lyophilised naloxone in the form of rapiddispersal wafers. This innovative approach aims to address the shortcomings of existing

naloxone formulations by improving portability whilst maintaining, crucially, the speed of drug absorption and duration of action.

4.2. Scientific Rationale

Buccal delivery is a potential alternative for emergency drug administration, and the route has been successfully used as a mode of delivery for emergency midazolam in the treatment of status epilepticus by non-medical persons. (6,25,26) Applying a tablet to the inner cheek is straightforward and can be performed by both non-specialist bystanders and healthcare professionals in emergency situations. After naloxone is released from the dosage form, the buccal mucosa, a stratified epithelium 40–50 cells (500–600 μ m) thick, serves as the primary absorption barrier.

The vasculature of the buccal mucosa drains into the retromandibular, lingual, and facial veins, which then drain directly into the internal jugular vein and the systemic circulation via the superior vena cava (27–29). While the absorption rate of naloxone from the human buccal cavity is not well known, studies in rats have shown a bioavailability of 70% from buccal administration compared to 0.3% via the oral route, owing to extensive first-pass metabolism, with maximum plasma levels reached within 15 minutes (30). Additionally, sublingual administration of 2–8 mg of naloxone solution has been reported to induce opiate withdrawal in humans within 30 minutes (4,30).

Our feasibility work demonstrated that rapid-dispersal naloxone wafers can be produced, disintegrating within seconds (25). Following this proof-of-concept laboratory production of a novel amorphous instant disintegrating tablet of naloxone, we have more recently shown feasibility and stability in a manufacturing facility according to good manufacturing practice standards (recent unpublished report available on request, manufactured by Catalent, Swindon, utilising their Zydis® technology). The formulation, comprising mannitol, gelatin, and sodium bicarbonate, are integral elements of the naloxone instant disintegrating buccal tablet (25).

Our innovative ultra-portable, dose-flexible, rapid-dispersal concentrated naloxone buccal wafer meets the challenge by bringing portability, speed, and dose-flexibility to the emergency overdose situation. Impact and benefits include an increased likelihood of naloxone being present and administered, and greater preparedness for unexpected high-dose or multiple-victim overdose scenarios. These will fit into a wallet or purse, thereby remedying current poor carriage rates for naloxone (only 15-20%).

The proposed buccal naloxone wafers have extreme portability: universal carriage is thus realistic. Current forms of naloxone need to be carried in their own container for the pre-filled syringe, or in a cardboard box or plastic case for nasal sprays. In contrast, buccal naloxone will be inserted into a wallet or purse in the credit-card section, thereby integrated with daily living and without needing repeated decision-making to achieve good adherence. The World Health Organization's objective is that '90% of all those with take-home naloxone must have it on them, or near them, at time of future emergency need': but current naloxone carriage rates are only 10-20%. However, with ultra-portable buccal naloxone, the objective is realistic and potentially achievable. No current naloxone product even approaches this degree of portability.

Our recently completed Phase 1 feasibility testing met all five objectives. We demonstrated feasibility of production: stable lyophilised naloxone, dose range (1-4mg), dispersal (<3 seconds), multi-dose credit-card format, planned price below current formulations, and the

declared objective is to steer the process forward to become a product with low cost and wide availability.

Likewise, phase 1 acceptability studies were strong, with 85% of one of the target populations of drug user peers willing to administer buccal naloxone (versus 78% nasal, 60% IM), and with a willingness to carry buccal naloxone on their person at all times at 92% (versus 60% and 33% respectively).

In this new proposed healthy volunteer study, we will examine the blood levels achieved, and how rapidly, following administration of the novel buccal naloxone (at two doses) and sublingual (one dose) and we will compare these with plasma levels following administration of naloxone by current approved routes of IM (main reference route) and IN (secondary reference route). This will guide decision-making about any possible further attention needed to speed of absorption and/or overall absorption and half-life which will guide decisions about whether and how to proceed to future commercial product.

5. Trial Objectives and Design

5.1. Trial Objectives

Primary Objective

1. To characterize and compare the pharmacokinetic profile of a novel buccal formulation of naloxone in healthy volunteers with approved formulations (naloxone ampoule) as the injectable form, and Nyxoid[®] as naloxone nasal spray comparison.

Secondary Objectives

- 1. To measure the dose-proportionality of the novel formulation by comparing the plasma exposure of two different buccal doses and one sublingually.
- 2. To assess the safety and tolerability of the novel buccal formulation

5.2. Primary endpoints

The primary endpoint will be Time to Maximum Plasma Concentration (T_{max}).

The time to reach maximum plasma concentration will be determined to characterize the rate of naloxone absorption. T_{max} will be reported as the median and range for each treatment group, based on observations over the 4-hour post-dose period.

5.3. Secondary endpoints

The following secondary endpoints will be assessed to provide a comprehensive pharmacokinetic profile of the novel buccal and sublingual naloxone formulation in comparison to the IM and IN reference formulations:

Time to 50% of maximum concentration (T50%)

A particularly important secondary endpoint will be the time taken to reach 50% of the observed C_{max} as the increase in plasma levels before reaching C_{max} is unlikely to be linear and we consider the time taken to reach 50% with different formulations is likely to give an

indication of the speed with which there may be future benefit of reversal of opioid overdose. T50% will be reported as the median and interquartile range for each treatment group, based on observations over the 4-hour post-dose period.

Maximum Plasma Concentration (C_{max})

The maximum observed plasma naloxone concentration will be determined for each formulation and dose. C_{max} will be reported as the mean and standard deviation for each treatment group, based on measurements taken over the 4-hour post-dose period.

Area Under the Curve from time zero to infinity (AUCinf)

The total systemic exposure to naloxone will be quantified by calculating the area under the plasma concentration-time curve extrapolated to infinity. AUC_{inf} will be reported as the mean and standard deviation for each treatment group, calculated from time zero to infinity.

Area Under the Curve from time zero to 15 minutes (AUC₀₋₁₅)

Early systemic exposure to naloxone will be assessed by calculating the area under the plasma concentration-time curve from administration to 15 minutes post-dose. AUC₀₋₁₅ will be reported as the mean and standard deviation for each treatment group.

Elimination Half-life (t_{1/2})

The elimination half-life of naloxone will be calculated from the terminal slope of the log concentration-time curve. $t_{1/2}$ will be reported as the mean and standard deviation for each treatment group over the 4-hour post-dose period.

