6.1. Investigational Medicinal Product

The study will use three formulations of naloxone:

- 1. Novel rapid-dispersal buccal and sublingual naloxone wafer (IMP)
- 2. Intramuscular naloxone (IM naloxone), standard product
- 3. Intranasal spray naloxone (IN naloxone), standard product

Novel rapid-dispersal buccal and sublingual naloxone wafer:

The investigational product is a novel rapid-dispersal ultra-portable formulation of naloxone hydrochloride (HCI) in wafer form. It will be tested at two doses: 2mg and 4mg (2 x 2mg wafers) administered buccally, along with a 2mg dose administered sublingually. The excipients include mannitol, gelatine and purified H2O. The wafers will be manufactured and supplied by Catalent, utilising their established Zydis[®] technology platform.

Comparators: Naloxone as IM injection and IN spray

The IM formulation will be a naloxone ampoule which contains naloxone hydrochloride as a 0.4mg/1ml. The IN spray formulation will be Nyxoid[®], containing 1.8mg/0.1mL naloxone hydrochloride dihydrate, equivalent to 2 mg of naloxone hydrochloride, per dose.

The 0.4mg IM dose is widely recognized as the standard initial dose for opioid overdose reversal in clinical practice. (1,31) Multiple studies have demonstrated the safety and efficacy of this dose in both clinical and healthy volunteer settings. (32,33) Using this standard dose allows for a direct comparison with real-world clinical use, enhancing the translational value of our study.

The 1.8mg/0.1mL IN naloxone dose (Nyxoid®) was selected based on the following rationale: a) This is the approved dose for the Nyxoid® nasal spray in Europe and other regions. (34) b) Studies have shown that this dose provides plasma concentrations over the first 10 minutes comparable to the 0.4mg IM dose, which is crucial for our comparative pharmacokinetic analysis. (35,36) c) Higher doses of naloxone have been widely used clinically in the US with

the 4mg spray (Narcan) being the most widely used product, and even higher doses of IN naloxone (up to 8mg) have been approved in the US for clinical use, and 8 mg nasal spray Kloxxado. (33,37,38)

For the naloxone wafer, we anticipate bioavailability comparable to the nasal spray and the maximum dosage being administered in the healthy volunteers' study is at half the level contained within the recently approved 8 mg naloxone nasal spray in the US.

6.1.1. Packaging and Labelling:

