The minimum washout period between drug administrations will be 36 hours (naloxone's half-life is <2 hours). A participant could therefore complete all study visits in stage 1, including follow-up, within three weeks.

The maximum period of each participant's participation is expected to be less than three months. If a participant has not completed all dosing sessions within this period, the screening visit will be repeated to ensure that they continue to meet all inclusion/exclusion criteria.

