8.2.1. Screening Visit

The screening visit will be performed at a maximum of 28 days prior to IMP administration/Visit 1. At the end of the visit, each participant will be provided with a card detailing emergency contact details.

The following interventions and assessments will be completed in order:

- i. Informed consent
- ii. Collection of demographic information
- iii. Medical review and physical examination (including review and documentation of current medications).
- iv. Height, weight, BMI
- v. Review of eligibility
- vi. Urine sample for urinalysis, pregnancy, and illicit drug testing (see section 8.3 for full list)
- vii. Alcohol breath test
- viii. Blood tests: LFTs; FBC & U&Es (see section 8.3 for full list)
- ix. Vital Signs
- x. ECG

8.2.2. Visits 1-5: Experimental visits for Stage 1

- 1. Randomisation to the treatment schedule ordering at or before Visit 1 as per Section 7.5 and Section 11.3.
- 2. Administration of IMP:

As this is an open-label study, participants will be informed of the dosing schedule. There will be a minimum 36 hrs washout between experimental visits.

For all five visits, the administration site will be checked pre-dose, and 30min & 4h post.

For buccal and sublingual IMP formulations, wafer disintegration time will be measured.

3. VAS:

Participants will complete a 100mm VAS immediately after administration of each formulation to assess taste and local tolerability.

4. Blood sampling:

Given the special interest in early absorption, blood collection included intense sampling during the first 15 minutes, with a total of 14 samples per session (pre-dose, at 2, 4, 6, 8, 10, 12.5, 15, 30 and 45 minutes and 1, 1.5, 2, 4 hours post-dose).

5. Vital signs:

Vital signs (HR, RR, BP, Temp) will be recorded on experimental visits at the following times: pre-dose, 10 minutes, 30 minutes, 1 hour, and 4 hours.

6. Adverse events and conmed checks:

Participants will be asked to report adverse events at specific timepoints (pre-dose, 10 minutes, 30 minutes, 1 hour, and 4 hours) during each experimental visit. Additionally, participants will be instructed that they can report any adverse events to the research

team at any time throughout their participation in the study. Conmed checks will be checked along with AEs.

The following interventions and assessments will be completed in order:

- i. Eligibility review
- ii. Review of any new medications or changes in medication since last visit

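### T50% is taken against each profile's own peak, so it describes absorption shape and should not be read alone as speed of possible reversal benefit

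*Protocol*

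**What the plan says.** Section 5.3 introduces T50% with the words "A particularly important secondary endpoint will be the time taken to reach 50% of the observed" Cmax. It gives as the reason that the time to 50% with different formulations is likely to give an "indication of the speed with which there may be future benefit of reversal of opioid overdose". The reporting rule is that "T50% will be reported as the median and interquartile range for each treatment group".

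The same section fixes the reference level: "The maximum observed plasma naloxone concentration will be determined for each formulation and dose". Each profile is therefore measured against its own peak. The protocol sets no common concentration level for any time endpoint.

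The products differ widely in dose. Section 6.1 says of the wafer: "It will be tested at two doses: 2mg and 4mg (2 x 2mg wafers) administered buccally, along with a 2mg dose administered sublingually". It says of the main comparator: "The 0.4mg IM dose is widely recognized as the standard initial dose for opioid overdose reversal in clinical practice".

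Three other provisions bear on the point. Section 5.4 lets a wafer arm continue to stage 2 only if its AUC0-15 is at least 90% of that of the IM ampoule. Section 5.3 also lists Cmax and AUC0-15 as secondary endpoints. Section 11.3 summarises T50% descriptively and keeps model-based inference for AUC and Cmax.

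**The concern.** How soon a product might help depends on when the plasma concentration reaches some given level, whatever that level is. T50% uses a different level for each profile. A product with a low early peak has a low target and can meet it quickly. A product with a high later peak has a high target and can meet it slowly, even if it passed every lower level first.

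The interpretation in section 5.3 is at stake. A reader who takes T50% on its own as speed of possible benefit could order the formulations wrongly against IM, and would see no gain in speed from 4 mg over 2 mg when there is one.

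**Working it through.** **Step 1. The general result.** Write a profile as C(t) = F·D·g(t), with bioavailability F, dose D and shape g. Then Cmax = F·D·max g. The condition C(t) = 0.5·Cmax becomes g(t) = 0.5·max g, so F and D cancel. This needs linear kinetics and the same g at both doses, but no numerical value. By contrast, the time to a fixed level L solves g(t) = L/(F·D), which comes earlier as F·D rises.

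**Step 2. Inputs for an illustration.** The protocol attaches no figure to T50%, so there is none to reproduce. It gives a half-life bound (section 6.2.1: "naloxone's half-life is <2 hours") and the sampling times (section 8.2.2: "pre-dose, at 2, 4, 6, 8, 10, 12.5, 15, 30 and 45 minutes and 1, 1.5, 2, 4 hours post-dose"). Section 4.2 says that human buccal absorption is not well characterised, so the rest is assumed: one compartment, first-order absorption, half-life 75 min, IM Tmax 15 min, and the wafer Tmax and systemic doses relative to IM shown in the table.

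**Step 3. Formulas.** ke = ln 2 / 75 = 0.00924 per min. ka is solved from Tmax = ln(ka/ke)/(ka − ke). In units of the IM value of F·D/V, with relative systemic dose d:

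C(t) = d·ka/(ka − ke)·[exp(−ke·t) − exp(−ka·t)] and Cmax = d·exp(−ke·Tmax)

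- IM: Cmax = exp(−0.00924 × 15) = 0.871, so half the IM peak is 0.435.
- Low-peak wafer: Cmax = 0.4 × exp(−0.00924 × 10) = 0.365. This is 42% of IM and below 0.435, so half the IM peak is never reached.
- High-exposure wafer: Cmax = 2 × exp(−0.00924 × 20) = 1.66, which is 1.9 times IM.
- The same wafer at half the dose: Cmax = 0.83, or 95% of IM.

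**Step 4. Results.**

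| Profile | T50%, own peak (min) | Time to half the IM peak (min) | AUC0-15 vs IM | Meets 90% criterion |
|---|---|---|---|---|
| IM, Tmax 15, d = 1 | 2.6 | 2.6 | 100% | reference |
| Wafer, Tmax 10, d = 0.4 | 1.6 | not reached | about 46% | no |
| Wafer, Tmax 20, d = 1.0 | 3.7 | 4.0 | about 85% | no |
| Wafer, Tmax 20, d = 2.0 | 3.7 | 1.7 | about 169% | yes |

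On the protocol's sampling times with linear interpolation, the times are 2.7 for IM, 1.7/not reached, 3.7/4.0 and 3.7/1.7 min. The orderings do not change.

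**Step 5. A second set of assumptions.** Take an IM absorption half-life of 5 min with F = 1, a volume of 200 L (which cancels in every comparison), and elimination half-lives of 60, 90 and 119 min, all on the protocol's sampling times.

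- Low peak: 2 mg wafer, F = 0.02, absorption half-life 3 min. T50% is 2.6 to 2.8 min against 3.7 to 4.2 min for IM. The wafer has about 11% of the IM Cmax and never reaches half of it.
- High exposure: 4 mg wafer, F = 0.3, absorption half-life 10 min. T50% is 6.6 to 7.5 min, slower than IM, but half the IM peak is reached at 2.0 to 2.3 min.
- Both doses of that wafer at a half-life of 90 min: T50% is 7.11 min at 2 mg and at 4 mg (IM 3.93). The time to half the IM peak is 4.78 min at 2 mg and 2.16 min at 4 mg. AUC0-15 is 16.28/16.54 = 98% and 32.56/16.54 = 197% of IM, so both doses would continue to stage 2 with the same T50%.

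**The case against.** The case for leaving the text alone is considerable. T50% against own Cmax is openly defined and is a legitimate measure of absorption rate. The sentence in section 5.3 is hedged. No test, margin or selection rule uses T50%. The illustration is wholly assumed, and differences of about 1 min are small beside early samples 2 min apart. Half the IM peak has no established clinical standing either, and a supplementary derived variable is often left to the SAP.

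Most of this stands, and it rules out three stronger readings that a reader might infer:

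- **That T50% is the protocol's measure of speed.** It is called one particularly important secondary endpoint. Tmax is primary and is meant to characterise absorption rate (section 5.2), and AUC0-15 covers early exposure.
- **That a weak wafer could advance by looking fast.** Selection rests on AUC0-15 alone, and the low-peak example, at about 46% of IM, would be dropped.
- **That the trial cannot show a benefit of the higher dose.** Cmax and AUC0-15 show it directly, and dose-proportionality is assessed on exposure (section 5.1). Even for T50%, equality of the two doses is exact only with linear kinetics and an unchanged shape. The 4 mg dose is two wafers, one in each cheek (section 6.2), so the shape could differ somewhat.

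The objection does not remove the cancellation itself, which follows from the definition and not from the assumed numbers. Nor does it remove the case of a high-exposure wafer that passes the 90% criterion and looks slower than IM. Tmax does not help there, since it is also free of dose and bioavailability under linear kinetics. The wording that invites the reading is in the protocol, whatever the SAP adds.

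**Conclusion.** The point holds as one of interpretation. Under linear kinetics with the same absorption shape, T50% is unaffected by dose or bioavailability, and its order against IM can be the reverse of the order on time to a common level. In the main illustration, a wafer with 1.9 times the IM peak is about 1 min slower than IM on T50% (3.7 against 2.6 min) and about 1 min faster to half the IM peak (1.7 against 2.6 min). The sizes rest on assumed absorption parameters; the direction recurs under the second set of assumptions across half-lives of 60 to 119 min.

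The consequence is limited. T50% decides nothing, selection uses AUC0-15, and Cmax and AUC0-15 are reported beside it. This is a worthwhile and cheap improvement, not a threat to the trial's conclusions.

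**What to change.** 1. Keep T50% as a descriptive measure of absorption shape. Reword section 5.3 so that it is read together with AUC0-15 and Cmax, and not alone as speed of possible benefit.
2. Add a supportive derived endpoint: the time to reach 50% of the same participant's IM Cmax, by linear interpolation between samples, with sessions that do not reach it by 4 h treated as censored. Report per arm the proportion reaching it and the median time.
3. State that this level is a reference and not an established effective concentration.
4. State that it can be derived only for participants with an IM session. By design that is everyone who completes stage 1; in stage 2 it applies only if IM is retained.

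The cost is one or two sentences and one derived variable from samples already planned. The downsides are dependence on one other session per participant, censoring, and the same limit from 2-minute sampling that T50% has. The change is best made before any concentration data are seen.
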